8.3.6 SERIOUS ADVERSE EVENT REPORTING

All SAEs occurring during the study must be reported to the UNC IRB per the UNC IRB reporting requirements. A written report (Serious Adverse Event Report Form) will be submitted to DAIDS and DAIDS MO within 24 hours of site becoming aware of the SAE. Additional information will be supplied as requested. All SAEs occurring during the study will be reported to DAIDS following guidelines for expedited AE reporting and to the FDA according to their regulatory guidelines.

After 30 days following the last dose of study drug administration, only SAEs the study PI (or designee) considers related to study drug or a protocol procedure, should be reported. Information regarding SAEs will be submitted to the DAIDS on required SAE reporting forms, which must be completed and signed by the study PI or designee, and sent within 24 hours of the site becoming aware of the SAE.

All Grade 3 or Grade 4 AE/SAEs considered related to study drug must be followed until recovery to baseline or Grade 1 with the date of resolution recorded in the source documents. In addition, the

investigator should report all follow-up for reportable Grade 3 or Grade 4 AE/SAEs to the UNC IRB. Resolution of an event is defined as the return to pre-treatment status or stabilization of the condition with the expectation that it will remain chronic.

All SAEs that have not resolved by the end of the study, or that have not resolved upon discontinuation of the participant's participation in the study, must be followed until any of the following occurs:

- The event resolves.
- The event stabilizes.
- The event returns to baseline, if a baseline value/status is available.
- The event can be attributed to etiology other than the study drug or to factors unrelated to study conduct.
- It becomes unlikely that any additional information can be obtained (participant's or health care practitioner's refusal to provide additional information, or lost to follow-up after demonstration of due diligence with follow-up efforts).

Any event requiring hospitalization (or prolongation of hospitalization) that occurs during the course of a participant's participation in a study must be reported as an SAE, except hospitalizations for the following:

- Hospitalizations not intended to treat an acute illness or adverse event (e.g., social reasons such as pending placement in long-term facility).
- Surgery or procedure planned before entry into the study (must be documented in the source document).

The study PI (or designee) will be responsible for notifying the FDA, VRC, and Merck, Inc. of any unexpected fatal or life-threatening suspected adverse reaction as soon as possible, but in no case later than 7 calendar days after the sponsor's initial receipt of the information. In addition, the sponsor must notify FDA in an IND safety report of potential serious risks, from clinical trials or any other source, as soon as possible, but in no case later than 15 calendar days after the sponsor determines that the information qualifies for reporting.

8.3.7 REPORTING EVENTS TO PARTICIPANTS

We are engaged in a number of similar studies of persistent HIV infection, using VOR and other interventions. We report the scientific findings of our work in the literature, and have regular (annual or more frequent) presentations with the local and national HIV+ and affected community. Due to the lack of evidence thus far that our studies have a clinical impact, we discuss the scientific findings in a general way with each participant after EOS visits. Our studies have extremely stringent stopping criteria, and thus far we have had no relevant or study-related SAEs to report. We would inform all study participants by letter or electronic messaging of any AEs determined by the External Study Safety Monitoring Committee to merit such notice.

8.3.8 ADVERSE EVENTS OF SPECIAL INTEREST

An adverse event of special interest (AESI; serious or non-serious) is one of scientific and medical concern specific to the protocol team, for which ongoing monitoring and rapid communication to the protocol team is required. These events might warrant further investigation in order to characterize and

understand it. Depending on the nature of the event, rapid communication by the protocol team to the UNC IRB, FDA, NIH, and product manufacturers (i.e., regulators) might also be warranted.

AESI for this protocol include those listed below. Updates to AESI will be added as an amendment to this protocol.

- Systemic lupus erythematosus (SLE)
- Systemic sclerosis (SS) (Systemic sclerosis [SSc]), including diffuse systemic form and CREST syndrome
- Sjogren's syndrome (SS)
- Polymyositis/Dermatomyositis syndrome (PM/DM)
- Raynaud's syndrome
- Antiphospholipid antibody syndrome (APS)
- Idiopathic thrombocytopenic purpura (ITP)
- Crohn's disease
- Ulcerative colitis

8.3.9 REPORTING OF PREGNANCY

We do not anticipate women participants becoming pregnant as we exclude women of child bearing potential from study participation. However, we will do the following should a pregnancy occur on study.

If the participant becomes pregnant during the study, all study treatment must be discontinued immediately. Although not considered an adverse experience, it is the responsibility of investigators or their designees to report any pregnancy in a participant or participant's partner (spontaneously reported to them) that occurs during the study or within 6 weeks of completing the study. All participants or their partners who become pregnant must be followed to the completion/termination of the pregnancy. If the pregnancy continues to term, the outcome (health of infant) must also be reported to the UNC IRB, the DAIDS Medical Officer, and the FDA (US Food and Drug Administration).

If a male participant impregnates his partner while he is participating in this study, the pregnancy must be reported and the study PI (or designee) should make a concerted effort to follow the pregnancy and outcome. The study PI (or designee) will make every effort to obtain a medical release and a separate pregnancy outcome consent from the pregnant partner granting permission to follow the health of both the pregnant partner and her unborn child to the UNC IRB, DAIDS, VRC, Merck and FDA without delay and within 24 hours if the outcome is an SAE (e.g. death, abortion, congenital anomaly, or other disabling or life-threatening complication to the mother or newborn).

Pregnancy and pregnancy outcome will be recorded. Pregnancies that occur on study should be reported prospectively to The Antiretroviral Pregnancy Registry. More information is available at www.apregistry.com. [contact]; [contact].

Pregnancy Outcomes and Reporting

If a woman has completed the study or chooses to discontinue from the study before the end of the pregnancy, then site study staff should request permission via a separate pregnancy outcome consent to contact her regarding pregnancy outcomes at the end of pregnancy. If the information is obtained, pregnancy outcomes will be submitted at the end of the pregnancy.

Pregnant women will discontinue study treatment and will be encouraged to continue on study and complete the evaluations included in the post-treatment evaluation section. At the end of the pregnancy, outcome and adverse events for participant and infant will be recorded. If pregnancy is suspected in a woman on study after study treatment, then a pregnancy test should be obtained. If pregnancy is confirmed, then further study treatment will be discontinued and the woman should continue on study (off study medication) safety follow-up visits as noted in the SOE. Stored plasma/PBMC for stored plasma for virologic studies should not be obtained to minimize blood volume. The site study staff should request permission via a separate pregnancy outcome consent to contact her regarding pregnancy outcomes at the end of pregnancy. A visit 6 months following the end of pregnancy will be conducted to assess for evidence of adverse events (AEs) in the participant and infant and documented.

8.4 NEW SAFETY INFORMATION

8.4.1 DEFINITION OF NEW SAFETY INFORMATION (NSI)

The Office for Human Research Protections (OHRP) considers new safety information involving risks to participants or others to include, in general, any incident, experience, or outcome that meets **all** of the following criteria:

- Unexpected in terms of nature, severity, or frequency given (a) the research procedures/study treatment that are described in the protocol-related documents, such as the Institutional Review Board (IRB)-approved research protocol, the informed consent document and Investigator’s Brochure (IB); and (b) the characteristics of the participant population being studied;
- Related or possibly related to participation in the research (“possibly related” means there is a reasonable possibility that the incident, experience, or outcome may have been caused by the procedures/treatment involved in the research); and
- Suggests that the research places participants or others at a greater risk of harm (including physical, psychological, economic, or social harm) than was previously known or recognized.

8.4.2 NEW SAFETY INFORMATION REPORTING

The investigator will report NSI to the UNC IRB. The NSI report will include the following information:

- Protocol identifying information: protocol title and number, PI’s name, and the IRB project number;
- A detailed description of the event, incident, experience, or outcome;
- An explanation of the basis for determining that the event, incident, experience, or outcome represents the NSI;
- A description of any changes to the protocol or other corrective actions that have been taken or are proposed in response to the NSI.

To satisfy the requirement for prompt reporting, NSIs will be reported using the following timeline:

- NSIs that are serious adverse events (SAEs) will be reported to the IRB and the DAIDS MO within 3 business days of the investigator becoming aware of the event.
- Any other NSIs will be reported to the IRB and to the DAIDS MO within 7 business days of the investigator becoming aware of the event.
- All NSIs should be reported to appropriate institutional officials (as required by an institution's written reporting procedures), the NIH MO (or designee), and the Office for Human Research Protections (OHRP) within 30 business days of the IRB's review and determination that the report of the problem from the investigator imposed a safety risk.

8.4.3 REPORTING NEW SAFETY INFORMATION TO PARTICIPANTS

We would inform all study participants by letter or electronic messaging of any NSI if it is determined by the UNC IRB to merit such notice.

9 STATISTICAL CONSIDERATIONS

This is a phase I, single-site study to evaluate the safety of VRC07-523LS combined with VOR in HIV-infected individuals suppressed on ART. There are secondary analyses to measure the effect of this therapy on persistent HIV-1 infection. All eligible participants will receive the same treatment which includes two (2) VRC07-523LS infusions and twenty (20) doses of VOR 400 mg. Participants will continue their baseline ART regimen throughout the study.

9.1 STATISTICAL HYPOTHESES

Hypothesis

Combination therapy with VRC07-523LS administered by IV infusion in combination with multiple doses of VOR 400mg orally will be safe and well tolerated.

9.2 SAMPLE SIZE DETERMINATION

We will enroll up to 12 fully evaluable participants (who receive two cycles of VRC07-523LS and VOR) to examine the effect of adding VOR and VRC07-523LS to ART on persistent replication-competent HIV within resting CD4+ T cells.

Any participant who does not complete both series of VRC07-523LS and VOR and the leukapheresis in Step 4 for reasons other than a grade 3 or higher AE will be replaced, to ensure up to 12 evaluable participants for safety.

Since the trial will be stopped if two participants experience a study treatment-related toxicity of Grade 3 or higher, the criterion for safety is grade 3 or higher toxicity in no more than 1 of 12 participants in the study.

For n=12 participants, if there are no primary AEs, then the exact 95% 1-sided upper confidence limit (UCL) for the true AE rate will be 0.22. Thus, if no AEs are observed, one can confidently rule out event rates greater than 22%.

All other analyses are therefore equally exploratory.

Because a focus of the study is on safety and potential AEs, accrual will be staggered such that enrollment and treatment administration will include a maximum of 1 participant per week.

9.3 POPULATIONS FOR ANALYSES

All participants who receive at least one dose of study therapy will contribute to the safety analysis of this study.

9.4 STATISTICAL ANALYSES

9.4.1 GENERAL APPROACH

We plan a phase I, single-center study in participants with HIV-1 infection who are receiving ART. Baseline ART will be maintained throughout the study. HIV-1 infected participants with plasma HIV RNA stably below the limit of quantitation will be screened. After meeting all eligibility criteria and enrollment, all participants will undergo an initial evaluation of resting CD4⁺T cells obtained via leukapheresis. A baseline measurement of the frequency of HIV-1 infection per million units (IUPM) in resting CD4⁺ cells will be performed by QVOA.

In Step 2, all participants will receive one (1) IV infusion of VRC07-523LS 40mg/kg, followed by ten (10) doses of VOR 400 mg PO every 72 hours. This exact cycle of a single VRC07-523LS 40mg/kg infusion followed by ten (10) doses of VOR 400 mg PO every 72 hours is repeated in Step 3. Therefore all participants will receive a total of 2 IV infusions of VRC07-523LS and 20 doses of VOR 400mg PO over a 3 month period. Participants completing this protocol will receive no more than a total of 8,000 mg of VOR. For reference, participants who completed a prior multi-dose study (58) received a total of 10,000 mg of VOR without clear evidence of any durable drug-associated toxicity, and no AEs greater than Grade 1.

Following Step 3, a leukapheresis will be performed approximately 1- 4 weeks after the last dose of VOR to measure the frequency of HIV-1 infection (IUPM) by QVOA.

Each participant will be followed for approximately 26 weeks once Step 2 begins.

Formal interim analyses will be performed at 6 month intervals during the conduct of this study, and will be reviewed by an independent Safety Monitoring Committee (SMC). If an interim analysis has not yet been performed, the Committee will perform a preliminary review of accumulated safety data after 4 participants have completed the first series of combined treatment with VRC07-523LS and 10 doses of VOR. This review will be based on assessment of participant safety, and will serve as a basis for allowing enrollment to continue. The Committee also will oversee all subsequent analyses.

9.4.2 ANALYSIS OF THE PRIMARY SAFETY ENDPOINT

Safety:

For the primary safety analysis, AEs attributed to study treatment will be described through the end of study visit approximately 20 weeks after getting their first infusion at Day 0. All participants who have been exposed to at least one dose of study treatment will be included in this analysis.

Since the trial will be paused for SMC review if two participants experience a study treatment-related toxicity of Grade 3 or higher, the criterion for safety of this study is grade 3 or 4 toxicity in no more than 1 of 12 participants.

9.4.3 ANALYSIS OF THE OTHER ENDPOINT(S)

Other Activity Endpoints:

- **Change in the frequency of HIV infection per million resting CD4⁺T cells (RCI) from baseline to after treatment with VRC07-523LS and VOR**

We will analyze pre-VOR/VRC07-523LS and post- VOR/VRC07-523LS frequency of HIV infection per million resting CD4⁺T cells using a non-parametric 2-sided sign test (supplemented by longitudinal regression modeling to estimate the magnitude of changes) to determine whether or not a significant decrease of IUPM is observed. With 12 participants, there will be 80% power to reject H₀ (change expected with ART alone) in favor of H_A (greater change than expected with ART) if the true probability of observing a decrease in IUPM in a participant after VOR/VRC07-523LS is 0.93.

This is based on a 2-sided alpha = 0.05 and the assumption that observed HIV infection frequency would decrease with probability 0.54 on ART alone after 6 months without intervention, based on the decay of IUPM seen on ART alone [Crooks 2015, Siliciano 2003].

In addition to summarizing the number and proportion of participants who show decrease in IUPM after VOR/VRC07-523LS, we will describe the magnitude of the changes in decrease in IUPM after VOR/VRC07-523LS via the median fold-change and corresponding 95% confidence interval. We will also summarize the proportion of participants with >6-fold decreases; this magnitude change is rarely seen in participants on stable ART [9].

Other Endpoints: Activity

- **HIV-1 RNA by low level viremia assay measurement at baseline and after treatment with VRC07-523LS and VOR**

The virologic analysis will include estimation of the low level viremia levels at pre-treatment (screening and entry) and separately at post-treatment. We assume that the probability would be 0.10 (10%) for a baseline (pre-entry, entry) detectable low level viremia ≥ 1 copy. The assumption that 10% of participants with a quantifiable low level viremia at screening will have low level viremia assay below the limit of detection at a pre-treatment measure is an estimate based on data from A5244 in which 6 of 50 (12%) enrolled participants had undetectable low

level of viremia at pre-entry and 5 of 51 (10%) at entry after having a screening low level of viremia ≥ 1 copy (59).

Other Exploratory Analyses:

- Following VOR/VRC07-523LS we will also explore whether there is a *depletion* of rc-RNA using the same statistical tests in the reverse (compare baseline rc-RNA to after two cycles of VOR/VRC07-523LS).
- To assess these within each individual participant (n of 1 analyses), we will use the non-parametric 2-sided Wilcoxon rank sum test to determine whether or not a statistically significant change in rc-RNA expression is observed, comparing rc-RNA levels measured in each of 24-36 replicate pools of 1 million resting CD4⁺ cells. Pools with undetectable RNA will be considered as 0 copies and analyzed as the lowest rank in this rank-based statistical test.

The pre-VOR rc-RNA expression will be determined as the median RNA copies over the individual pools of one million participant cells tested prior to VOR (setting undetectable RNA pools as 0 copies), and the post-VOR RNA expression level will be similarly determined. Changes in RNA expression will be evaluated by the exact sign test and the proportion of participants with increases versus decreases. Summaries of the magnitude of changes will be examined in terms of median fold-changes.

- We will also explore changes in the chromosomally integrated viral reservoir as measured by Q-PCR from baseline to post VOR/VRC07-523LS.
- We will also explore the change in frequency of viral envelope sequences detected in plasma or cells that are not recognized by VRC07-523LS from baseline to post VOR/VRC07-523LS.
- A 0.05 significance level will be used throughout, with no adjustment for multiple testing given the proof of concept nature of this study. Emphasis will be put on estimation with corresponding 95% confidence intervals to evaluate the scientific and biologic effect size. Individual-level data will be visualized in plots. Given the small sample size, exploratory analyses will have limited or no statistical power and findings should be interpreted with caution and assessed in a subsequent, larger study if the combined treatment is found to be safe and potentially efficacious. If the study is stopped at n=12 participants, statistical analyses will be limited to descriptive summaries and n of 1 analyses within each participant.

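### The IUPM analysis is called a sign test (by convention against 0.5), but the stated 80% power belongs to an equal-tailed exact test against 0.54 that needs 11 of 12, so the call at exactly 10 of 12 is left open

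*Combined protocol and SAP*

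**What the plan says.** Section 9.4.3 (Analysis of the Other Endpoint(s)) compares IUPM before and after treatment "using a non-parametric 2-sided sign test", supplemented by regression modelling, "to determine whether or not a significant decrease of IUPM is observed". That sentence gives no null probability, no method for the two-sided p-value, no rejection count and no rule for ties.

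The power statement follows. It takes H0 to be the change expected on ART alone and says that with 12 participants "there will be 80% power to reject" it "if the true probability of observing a decrease in IUPM in a participant after VOR/VRC07-523LS is 0.93". The basis is then given: "This is based on a 2-sided alpha = 0.05", and an assumption that infection frequency "would decrease with probability 0.54 on ART alone after 6 months without intervention".

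Three other places bear on the weight of this test:
- Section 8.1 (Resting CD4 T Cell Infection) says that a statistically significant decline would be definitive evidence that the reservoir had shrunk.
- Section 9.2 describes every analysis other than the primary safety analysis as exploratory.
- The last bullet of 9.4.3 puts the emphasis on estimates with 95% confidence intervals. It also restricts a study stopped at 12 participants to descriptive summaries and within-participant (n of 1) analyses.

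**The concern.** A sign test, as usually understood, tests whether decreases and increases are equally likely, that is, a probability of 0.5. The plan's own null is 0.54. An analyst who runs the named test literally would therefore test a different null from the one in the power statement. The same section later uses an exact sign test for RNA expression with no ART-alone probability attached, which makes a reading of 0.5 more likely to be carried across.

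Setting the null at 0.54 does not settle the matter by itself. The null binomial distribution is then asymmetric, and the common ways of forming a two-sided exact p-value differ. With 12 participants, the choice of null and the choice of two-sided method each move the rejection count between 10 and 11.

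What is at stake is whether 10 decreases among 12 participants is reported as a significant fall in the reservoir. Because Section 8.1 gives so much weight to significance, the rule should be fixed before the data are seen.

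**Working it through.** **Inputs, all from 9.4.3:** n = 12; null probability of a decrease p0 = 0.54; alternative p1 = 0.93; two-sided alpha 0.05; stated power 80%. The value 0.5 is the convention for a sign test and is not a figure in the plan. X is the number of participants with a decrease, taken as binomial(12, p).

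**1. Reproduce the stated power.** Upper tails under 0.54:
- P(X ≥ 10) = 66 × 0.54^10 × 0.46^2 + 12 × 0.54^11 × 0.46 + 0.54^12 = 0.0294 + 0.0063 + 0.0006 = 0.0363
- P(X ≥ 11) = 0.0063 + 0.0006 = 0.0069

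With at most 0.025 allowed in the upper tail, the smallest rejection count is 11. Power at 0.93:
- P(X ≥ 11) = 12 × 0.93^11 × 0.07 + 0.93^12 = 0.378 + 0.419 = 0.797

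This agrees with the stated 80%.

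**2. Power if 10 of 12 were enough.** Add P(X = 10) = 66 × 0.93^10 × 0.07^2 = 0.157. Power becomes 0.797 + 0.157 = 0.953. Every rule that rejects at 10 has this power, so the stated 80% needs the rule of 11. An uncorrected normal approximation does not give 80% either (0.929 against 0.54, 0.977 against 0.5).

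**3. Two-sided p-value at 10 of 12 under each reading.**
- Sign test against 0.5: 2 × (66 + 12 + 1)/4096 = 0.0386
- Exact test against 0.54, minimum likelihood (adding all outcomes no more probable than the one observed, here X ≥ 10 and X ≤ 2): 0.0363 + 0.0095 = 0.0459
- Exact test against 0.54, twice the smaller tail: 2 × 0.0363 = 0.0727

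A continuity-corrected normal test against 0.54 gives 0.080 and so leads to the same count as the doubled tail.

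**4. Side by side.**

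| Reading | Rejects for a decrease at | p at 10 of 12 | Upper tail under 0.54 | Total two-sided size under 0.54 | Power at 0.93 |
|---|---|---|---|---|---|
| Sign test, null 0.5 | ≥ 10 | 0.039 | 0.036 | 0.046 | 0.953 |
| Exact, null 0.54, minimum likelihood | ≥ 10 | 0.046 | 0.036 | 0.046 | 0.953 |
| Exact, null 0.54, twice the smaller tail | ≥ 11 | 0.073 | 0.007 | 0.016 | 0.797 |

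All three readings reject on the other side at 2 or fewer, which adds 0.0095 to the size. At 11 of 12 all three are significant (equal-tailed p = 0.014).

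**5. How often it matters.** Only a count of exactly 10 changes the call. Its probability is 0.029 if the true probability is 0.54 and 0.157 if it is 0.93. The probability of a decrease that gives 80% power is 0.87 under the 10-of-12 rule and 0.93 under the 11-of-12 rule.

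**The case against.** The strongest reply is that 9.4.3, read as a whole, describes one test. The sentence after the test is named defines the null as the ART-alone change, and 0.54 follows. On that view the plan leaves out a p-value method but does not contain two tests. This stands in part. A reader might infer that the plan itself states a null of 0.5; it does not, and that value comes only from the usual meaning of the test's name. It remains true that the test run literally under that name is not the one that was powered, and that even with 0.54 fixed the result at 10 of 12 is undetermined.

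A reader might also infer that the 10-of-12 rule breaks the stated alpha. It does not. The plan asks only for a two-sided 0.05 and says nothing about equal tails, and the total size under 0.54 is 0.046. The upper-tail error of 0.036 is above 0.025 only if equal tails are required. Nor is the trial underpowered on any reading, since the departure is upward, from 80% to 95%. A claim that the outcome turns on software defaults has no basis either, because the plan names no software.

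Finally, the reach is narrow. The endpoint is exploratory, fold-changes with confidence intervals will be reported alongside, and the closing bullet of 9.4.3, taken literally, rules out this across-participant test in a study stopped at 12. These points lower the priority. They do not remove the ambiguity, and the last one is a further inconsistency with a power statement written for 12 participants.

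**Conclusion.** The point holds as a mismatch between the test named and the test powered. Among the exact tests considered, the stated 80% power belongs to the equal-tailed test against 0.54 with rejection at 11 or more of 12 (power 0.797, upper tail 0.007). The conventional sign test and the minimum-likelihood test against 0.54 both reject at 10 (power 0.953, upper tail 0.036, total size 0.046). The practical consequence is one outcome, exactly 10 of 12, which is called significant at 0.039 or 0.046, or not significant at 0.073.

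This assumes 12 evaluable participants, independent outcomes, no ties and the plan's own 0.54, which cannot be checked from the documents. Priority is modest because the endpoint is exploratory. It is still worth settling, given the evidential weight that Section 8.1 places on a significant decline.

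**What to change.** In 9.4.3, replace the reference to a sign test for IUPM with wording such as: exact binomial test of the number of participants with a decrease against 0.54, two-sided p equal to twice the smaller tail; at n = 12 a decrease is significant at 11 or more. This matches the power statement as it stands. The cost is giving up a significance claim at 10 of 12.

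Alternatively, keep a 10-of-12 rule, name the null and the two-sided method that produce it, and restate the power as 95% at 0.93. The cost is a revised power statement.

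Two related points:
- No tie rule is proposed here. The documents do not show how ties were counted when 0.54 was derived, and a rule that did not match that derivation would make the null wrong. The sponsor should state the rule that fits its source.
- The closing bullet of 9.4.3, which limits a study stopped at 12 participants to descriptive and n of 1 analyses, should be reconciled with the test and power statement for 12 participants in the same section.

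The change is one or two sentences for the test plus this reconciliation, with no effect on study conduct.
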